8.2 Serious Adverse Events

An adverse event or adverse reaction is considered serious if, in the view of either the Investigator or Sponsor, it results in any of the following outcomes:

- Death,
- A life-threatening adverse event,
 - Note: An adverse event or adverse reaction is considered "life-threatening" if, in view of either the Investigator or Sponsor, its occurrence places the subject at immediate risk of death. It does not include an event that, had it occurred in a more severe form, might have caused death.
- Requires hospitalization or prolongation of existing hospitalizations,
 - Note: Any hospital admission with at least 1 overnight stay will be considered an inpatient hospitalization. An emergency room visit without hospital admission will not be recorded as a SAE under this criterion, nor will hospitalization for a procedure scheduled or planned before signing of informed consent. However, unexpected complications and/or prolongation of hospitalization that occur during elective surgery should be recorded as adverse events and assessed for seriousness. Admission to the hospital for social or

situational reasons (i.e., no place to stay, live too far away to come for hospital visits) will not be considered inpatient hospitalizations.

- A persistent or significant disability/incapacity or substantial disruption of the ability to conduct normal life functions,
- A congenital anomaly/birth defect, or
- An important medical event.
 - Note: Important medical events that may not result in death, be life-threatening, or require hospitalization may be considered an SAE when, based upon appropriate medical judgment, they may jeopardize the subject and may require medical or surgical intervention to prevent 1 of the outcomes listed above. Examples of such medical events include allergic bronchospasm requiring intensive treatment in an emergency room or at home, blood dyscrasias or convulsions that do not result in inpatient hospitalizations, or the development of drug dependency.

8.3 Serious Adverse Event Reporting – Procedures for Investigators

8.3.1 Initial Reports

All SAEs occurring from the time of the start of the investigational product infusion at Day 0 until Day 365 must be reported to Medpace Clinical Safety within 24 hours of the knowledge of the occurrence (this refers to any adverse event that meets any of the aforementioned serious criteria).

To report the SAE, complete the SAE form electronically in the Electronic Data Capture (EDC) system for the study. When the form is completed, Medpace Safety personnel will be notified electronically and will retrieve the form. If the event meets serious criteria and it is not possible to access the **EDC** system, e-mail Medpace Safety send an to [contact] or call the Medpace SAE hotline (phone number listed below), and fax the completed paper SAE form to Medpace (fax number listed below) within 24 hours of awareness. When the EDC system becomes available, the SAE information must be entered within 24 hours of the system becoming available.

Safety Contact Information: Medpace Clinical Safety

Medpace SAE reporting line – USA:

[contact], dial 3 or [contact], dial 3

[contact] or [contact]

E-mail: [contact]

Medpace SAE reporting line – Europe:

[contact]

[contact]

E-mail: [contact]

8.3.2 Follow-up Reports

The Investigator must continue to follow the subject until the SAE has subsided or until the condition becomes chronic in nature, stabilizes (in the case of persistent impairment), or the subject dies.

Within 24 hours of receipt of follow-up information, the Investigator must update the SAE form electronically in the EDC system for the study and submit any supporting documentation (e.g., subject discharge summary or autopsy reports) to Medpace Clinical Safety via fax or e-mail. If it is not possible to access the EDC system, refer to the procedures outlined above for initial reporting of SAEs.

8.3.3 Additional Reporting Requirements for Suspected Unexpected Serious Adverse Reaction

Athersys, Inc. is responsible for processing any suspected unexpected serious adverse reaction (SUSAR). The SUSARs are also referred to as alert reports, expedited safety reports, and investigational new drug safety reports.

A SUSAR is defined as any SAE that is determined to be associated with the use of study drug and is unexpected (not currently listed in the safety reference information [see the Investigator's Brochure] or is not listed at the specificity or severity that has been observed). Athersys, Inc. will notify all Investigators currently conducting MultiStem clinical studies of all SUSARs in accordance with applicable regulations. All SUSARs will be reported to the relevant regulatory authorities and IRBs/IECs according to the rules in effect in each country where study sites are located:

- If the SUSAR is fatal or life-threatening, regulatory authorities and ethics committees will be notified within 7 calendar days after Athersys, Inc. learns of the event.
- If the SUSAR is not fatal or life-threatening, regulatory authorities and ethics committees will be notified within 15 calendar days after Athersys, Inc. learns of the event.

These notifications will need to be filed in each site's study file and submitted to each site's IRB/IEC in accordance with policy.

Safety updates will be provided periodically to the regulatory authorities and IRBs/IECs responsible for the study according to the rules in effect in each country where study sites are located. These updates will include information on SUSARs and other relevant safety findings.

8.4 Pregnancy Reporting

If the subject or partner of a subject participating in the study becomes pregnant during the study, the Investigator should report the pregnancy to Medpace Clinical Safety within 24 hours of being notified. Medpace Clinical Safety will then forward the Exposure In Utero form to the Investigator for completion.

The subject or partner should be followed by the Investigator until completion of the pregnancy. If the pregnancy ends for any reason before the anticipated date, the Investigator should notify Medpace Clinical Safety. At the completion of the pregnancy, the Investigator will document the outcome of the pregnancy. If the outcome of the pregnancy meets the criteria for immediate classification as an SAE (i.e., postpartum complication, spontaneous abortion, stillbirth, neonatal death, or congenital anomaly), the Investigator should follow the procedures for reporting an SAE.

8.5 Expedited Reporting

The Sponsor will report all relevant information about suspected unexpected serious adverse reactions that are fatal or life-threatening as soon as possible to the FDA, applicable competent

authorities in all the Member States concerned, and to the Central Ethics Committee, and in any case no later than 7 days after knowledge by the Sponsor of such a case, and that relevant follow-up information will subsequently be communicated within an additional 8 days.

All other suspected unexpected serious adverse reactions will be reported to the FDA, applicable competent authorities concerned and to the Central Ethics Committee concerned as soon as possible but within a maximum of 15 days of first knowledge by the Sponsor.

The Sponsor will also inform all Investigators as required.

8.6 Medical and Surgical History

Medical history, including details regarding all illnesses and allergies, dates of onset, status of current condition, and smoking and alcohol use will be collected for all subjects at Screening (0 to 28 hours post-stroke). Additional information to be collected includes past surgical and medical procedures as well as medications.

8.7 Demographics

Demographic information including day, month, and year of birth (as permitted by country); race; and gender will be collected for all subjects at Screening (0 to 28 hours post-stroke).

8.8 Clinical Laboratory Evaluations

8.8.1 Standard Safety Laboratory Assessments

At Screening, a chemistry and hematology blood sample will be collected and analyzed at a local laboratory per the institutional requirements and local processes.

For the remainder of the study, starting at Day 0 (Baseline), chemistry and hematology blood samples will be collected and sent to a central laboratory.

Chemistry and hematology will be collected as marked in the Schedule of Procedures (Appendix A, Table 3). See the Laboratory Manual list of chemistry and hematology analytes.

Detailed procedures of sampling preparation, storage, and shipment will be described in a specific Laboratory Manual which will be provided to all sites.

The Investigator must review and sign all laboratory test reports. At Screening, subjects who have laboratory values that are outside the exclusionary limits specified in Section 4.2, may not proceed to randomization.

8.8.2 Pregnancy Test

A urine or serum pregnancy test (per standard of care) will be performed on female subjects of childbearing potential at Screening (0 to 28 hours post-stroke).

8.9 Vital Signs

Vital signs include blood pressure, pulse, respiratory rate, and temperature.

Vital signs will be collected at Screening (0 to 28 hours post-stroke), Baseline (Day 0) (pre- and post-infusion), 24 hours from the start of the infusion, 48 hours from the start of the infusion, Day 7, and Day 365/ET.

Note: Vital signs will be collected just prior to infusion start, but no more than 60 minutes prior; every 30 (\pm 5) minutes for the first 2 hours after the infusion start; and then at 4 hours (\pm 30 minutes) and 6 hours (\pm 30 minutes) after the infusion start.

8.10 Pulse Oximetry

Oxygen saturation (via pulse oximetry) will be collected at Screening (0 to 28 hours post-stroke), Baseline (Day 0) (pre- and post-infusion), 24 hours from the start of the infusion, 48 hours from the start of the infusion, Day 7, and Day 365/ET.

Note: Oxygen saturation (via pulse oximetry) will be collected just prior to infusion start, but no more than 60 minutes prior; every 30 (\pm 5) minutes for the first 2 hours after the infusion start; and then at 4 hours (\pm 30 minutes) and 6 hours (\pm 30 minutes) after the infusion start.

8.11 Electrocardiograms

A 12-lead ECG will be conducted at Screening (0 to 28 hours post-stroke), 24 hours from the start of the infusion, and 48 hours from the start of the infusion. Any clinically significant abnormalities will be captured as an adverse event.

8.12 Physical Examinations

A physical examination will be performed at Screening (0 to 28 hours post-stroke), Baseline (Day 0) (before infusion start), 24 hours from the start of the infusion, Day 30, and Day 365/ET.

The extent of the physical examination is at the discretion of the Investigator.

8.13 Height and Weight

Height will be collected at Screening. Height can be collected as the measured value or the reported value.

Weight will be collected at Screening.

9 STATISTICS

9.1 Analysis Populations

9.1.1 Intent-to-Treat Population

The Intent-to-Treat Population will include all randomized subjects. This population will be used for the primary and key secondary efficacy analyses.

9.1.2 Modified Intent-to-Treat Population/Safety Population

The Modified Intent-to-Treat Population will include all randomized subjects who receive study drug. Primary and key secondary efficacy analyses will be repeated using this population.

This population will also be used to summarize all safety data, and for safety analyses, will be referred to as the Safety Population.

9.1.3 Per Protocol Population

The Per Protocol Population will include all randomized subjects who do not have any violations or entry criteria or protocol deviations that could significantly impact the assessment or interpretation of efficacy data. Subject data will be reviewed by the clinical team to identify exclusions from the Per Protocol Population. The list of subjects to be excluded from the Per Protocol Population will be finalized prior to database unblinding.

9.2 Statistical Methods

A separate Statistical Analysis Plan will be prepared to provide additional details on the approach to analyses and data displays.

9.2.1 Analysis of Efficacy

9.2.1.1 Primary efficacy analysis

The primary efficacy variable will be the mRS score at Day 90. To compare the distributions of the mRS scores at Day 90, all mRS values (0 to 6) will be considered (except the categories 5 and 6 are collapsed into a single group). The proportion of subjects in each category will be summarized with counts and percentages and compared between the MultiStem group and placebo group. Specifically, the van Elteren test, an extension of the 2-sample Wilcoxon rank-sum test, stratified by Baseline NIHSS score (\leq 12 and \geq 13), use of concomitant reperfusion therapy (Yes or No), and age group (18 to 64 years and \geq 65 years) will be used for the primary comparison.

Furthermore, the probability that a randomly chosen subject who receives the MultiStem treatment will have a better mRS score than a randomly chosen subject from the same stratum receiving the placebo treatment, will be estimated. This measure does not depend on any parametric model assumption and was proposed by Howard et al., ¹⁶ as the consistent companion of van Elteren test. Specifically, for each stratum, each subject from the MultiStem group will be paired with each subject from the placebo group in order to determine the percentage of subject pairs where the MultiStem subject achieved a better mRS score and the percentage where the placebo subject achieved a better mRS score. The stratum-specific percentages by their corresponding weighted averages (weighted by the stratum size) will be combined and the estimated probabilities that the mRS score from a MultiStem subject is better and worse than that from a placebo subject in the

same stratum will be reported. The difference of these 2 probabilities will be used to measure the treatment effect. The confidence interval of the difference will be constructed based on large sample approximations for the distribution of related U-statistics.

For the primary analysis, the last observation carried forward (LOCF) approach will be applied to impute missing data, e.g., a missing mRS score at Day 90 will be imputed by the last observed post-Baseline mRS score prior to Day 90. Subjects who die prior to Day 90 will have a mRS score of 6 imputed for the Day 90 analysis.

As a supportive analysis, an alternative measure for the treatment effect, the odds ratio (OR) from a stratified proportional odds model, will be estimated as well. The proportional odds model assumes a constant OR with respect to the dichotomized mRS score using cut-off values of 1, 2, 3, 4, and 5. The 95% confidence interval for the OR will be constructed. Furthermore, multivariate regression analysis will be performed to adjust for potential imbalances in important Baseline characteristics other than the selected stratification factors based on the stratified proportional odds model.

Sensitivity analyses will be performed in order to evaluate the impact of missing data on overall study conclusions.

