9.2.5 Sample Size Determination

For this study, sample size and power are computed by assuming that the true proportions of subjects with various mRS outcomes at the 90-day follow-up visit are as displayed in Table 1.

Table 1. Estimates of Proportions of Subjects With Modified Rankin Scale Scores – 90-Day Follow-up Visit

	Modified Rankin Scale Score								
Group	0	1	2	3	4	5	6		
Treatment	4.0%	15.5%	28.9%	26.6%	17.5%	0.0%	7.4%		
Control	0.0%	6.8%	27.1%	29.7%	14.4%	5.8%	16.3%		

The rates used in the computations correspond to those observed in B01-02 for the population under study in B01-04, making minor adjustments to reflect expectations for subjects receiving both tPA and mechanical thrombectomy (limited to 10% of enrolled B01-04 study subjects). The power of unstratified Wilcoxon rank test was estimated using Monte-Carlo simulation. Based on this approach, a 1-sided alpha level of 0.025, 300 subjects provide 95% power for testing the study's primary effectiveness hypothesis. The power of van Elteren test adjusting for stratification factors will be even higher than this unstratified counterpart.

Other alternative outcome estimates were evaluated (a) adjusting the outcome above by reducing the treatment advantage over control, and (b) comparing an adjusted treatment outcome to placebo rates observed in other relevant studies. Several studies were identified with control populations representative of the targeted population for B01-04, taking into consideration stroke severity, concomitant treatments (e.g., tPA), timing of treatment, age, and functional outcomes.

These sensitivity analyses confirm that at 300 subjects (150 subjects per group), the B01-04 study would be adequately powered to test the hypothesis that MultiStem treatment can improve global disability as measured throughout the range of mRS scores by shift analysis.

Based on previous studies, the proposed study is expected to have a low dropout rate, outside of deaths. Among the subjects randomized in Study B01-02 (n=129), there were 23 who did not complete the study over 365 days. Among these, 3 subjects (2.3%) withdrew consent prior to dosing, 14 subjects died (10.9%), 5 subjects (3.9%) were lost to follow-up, and 1 subject (0.8%) was withdrawn by Investigator. In the proposed study, death is not considered a discontinuation, but rather the worst outcome for the mRS distribution analysis and a non-response for the binary analyses.

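### The supportive adjusted proportional-odds model should carry continuous Baseline NIHSS and age as prespecified covariates; the primary van Elteren test can stay as it is

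*Protocol*

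**What the plan says.** Section 9.2.1.1 fixes the primary comparison as a van Elteren test over three two-level factors: Baseline NIHSS (12 or less against 13 or more), concomitant reperfusion (yes or no) and age (18 to 64 against 65 and over), which makes eight strata. These are the randomization factors of Section 5.3 at the same cut-points. Section 9.2.1.2 uses the same strata for the Cochran-Mantel-Haenszel tests of the key secondary endpoints.

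A stratified proportional-odds model supplies a supportive odds ratio. Of its extended version Section 9.2.1.1 says that "multivariate regression analysis will be performed to adjust for potential imbalances in important Baseline characteristics other than the selected stratification factors".

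Section 9.2.5 says of planned power: "The power of unstratified Wilcoxon rank test was estimated using Monte-Carlo simulation". It then adds: "The power of van Elteren test adjusting for stratification factors will be even higher than this unstratified counterpart". That gain is not quantified.

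The finer data exist. Eligibility rests on a full NIHSS score from 8 to 20 (Section 4.1), the score is taken again at Baseline (Section 7.2.1), and date of birth is recorded as far as each country permits (Section 8.7).

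**The concern.** In a randomized trial any baseline imbalance is due to chance. What makes covariate adjustment efficient is how well the covariate predicts outcome, and that holds whether or not the arms happen to be balanced. The protocol gives imbalance as the reason for the adjusted model and points it at characteristics other than the stratification factors. A plan that follows this wording closely would leave NIHSS and age in the model only as dichotomies, so that NIHSS 13 and 20, or ages 65 and 90, count as alike.

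By stratifying on NIHSS and age, and by saying that adjustment for the strata raises power, the protocol itself treats both as prognostic. The same reasoning applies to whatever they predict within a stratum. At stake is the efficiency of the supportive odds ratio. It would matter most if the true effect were smaller than Table 1 assumes.

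**Working it through.** **1. The plan's own figure.** The protocol states that "a 1-sided alpha level of 0.025, 300 subjects provide 95% power for testing the study's primary effectiveness hypothesis". Inputs are the Table 1 rows (treatment 4.0, 15.5, 28.9, 26.6, 17.5, 0.0, 7.4%; control 0.0, 6.8, 27.1, 29.7, 14.4, 5.8, 16.3%; rescaled, since they sum to 99.9 and 100.1), 150 per group, and mRS 5 and 6 collapsed.

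- P(treated subject better) = 0.5117 and P(worse) = 0.2788, so P(better) + ½P(tie) = 0.5117 + ½(1 − 0.5117 − 0.2788) = 0.6164.
- Null SE = √[(N + 1)/(12·n·m) × (1 − Σp³)], with p the pooled category shares and Σp³ ≈ 0.053: √[301/(12 × 150 × 150) × 0.947] = 0.0325.
- z = 0.1164/0.0325 = 3.58; power = Φ(3.58 − 1.96) ≈ 94.8%.
- Monte-Carlo (40,000 runs) gives 95.5%, and 94.2% and 93.1% at 141 and 135 per group, against the stated 95%, 94% and 93%. The figure reproduces, and it uses no covariate adjustment at all.

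**2. How much information the cut-points leave behind.** Assumed, because the documents do not give it: NIHSS uniform on 8 to 20; age normal with mean 66 and SD 13; reperfusion in 40% with no effect of its own; a share R² of the latent mRS variance explained by NIHSS and age, split 60/40.

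- NIHSS: total variance (13² − 1)/12 = 14. Within strata: (5/13)(5² − 1)/12 + (8/13)(8² − 1)/12 = 0.77 + 3.23 = 4.0. Share left: 4.0/14 = 29%.
- Age cut at 65: c = (65 − 66)/13 = −0.077. Share captured: φ(c)²/[Φ(c)(1 − Φ(c))] = 0.1582/0.2491 = 64%. Share left: 36%.
- Weighted share left: w = 0.6 × 0.286 + 0.4 × 0.365 = 0.318.
- Approximate gain in effective sample size from adding the continuous values: R²·w/(1 − R²).

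**3. Simulation.** Table 1 margins were kept in each arm, with 1,000 trials per cell. The stratified proportional-odds model was fitted with stratum terms only, then with continuous NIHSS and age added. Gain = (mean z with continuous terms / mean z without)² − 1. The rejection rates are for this supportive model at 1-sided 0.025. The reduced effect is 72.5% of Table 1, which puts the unstratified test at about 75% power, the level of Case 2 in Table 2.

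| R² | Formula gain | Simulated gain, Table 1 effect | Simulated gain, reduced effect | Rejection %, Table 1 effect | Rejection %, reduced effect |
|---|---|---|---|---|---|
| 0 | 0% | 0.4% | 0.4% | 94.9 → 95.2 | 72.7 → 73.0 |
| 0.1 | 3.5% | 5.1% | 4.8% | 96.2 → 96.7 | 78.9 → 80.6 |
| 0.2 | 7.9% | 8.3% | 8.2% | 98.6 → 99.1 | 84.6 → 86.7 |
| 0.3 | 13.6% | 12.7% | 14.4% | 98.9 → 99.7 | 86.1 → 89.6 |
| 0.4 | 21.2% | 20.1% | 21.4% | 99.2 → 99.7 | 89.4 → 94.9 |

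The formula and the simulation agree closely. A gain of 5% to 20% corresponds to 0.05 × 300 = 15 up to 0.20 × 300 = 60 subjects. Each rejection rate carries a Monte-Carlo standard error of about 1 point: √(0.85 × 0.15/1000) = 0.011 at a rate of 85%.

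**4. Where the gain appears.** At R² = 0.3 with the Table 1 effect, the mean log odds ratio in favour of treatment moves from 0.905 to 0.976 and its mean SE from 0.214 to 0.218. Mean z rises from 4.21 to 4.47, and (4.47/4.21)² = 1.127. The SE does not shrink. The conditional estimate moves further from zero than its SE grows.

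**5. The primary test.** A rank analysis of covariance with continuous NIHSS and age gained between 0 and 2 points over van Elteren at R² from 0 to 0.4 (for example 80.4% to 82.3% at R² = 0.2 with the reduced effect; 3,000 runs). Under the null with R² = 0.3, both rejected 2.7% of the time (6,000 runs), near the nominal 2.5%.

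**The case against.** The best defence is that nothing here is wrong. The van Elteren test uses exactly the randomization factors at their randomized cut-points, holds its error rate, and is paired with a within-stratum pairwise probability that Section 9.2.1.1 selects as its matching effect measure. All of that stands. A reader might infer that the primary test should be replaced. The documents do not support that: the rank analysis of covariance adds at most about 2 points here, other assumed correlations give from under 1 point to 4 (the last only with the strongest pair, 0.5 for NIHSS and 0.3 for age), and the change would separate the test from its effect measure.

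A reader might also infer that covariates will be picked once imbalance has been seen. The text does not say so. It speaks of potential imbalance and important characteristics, and Section 9.2 leaves further detail to the SAP, where a covariate list may properly sit. Nor does the wording strictly bar continuous NIHSS or age, since the factors it sets aside are the two-level ones. It only fails to bring them in and points the model elsewhere.

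It might seem, too, that confirmatory power is being lost in the weaker cases of Table 2. Planned power rests on the unstratified test, and the supportive model carries no alpha, so changing that model recovers none.

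What remains is that the stated rationale and scope, followed as written, leave collected prognostic information out of the one model that could easily use it.

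**Conclusion.** The point holds as a low-cost improvement to a supportive analysis. The expected benefit is about 5% to 20% more effective sample size for the supportive odds ratio if NIHSS and age explain 10% to 40% of the latent Day 90 mRS variance, and none if they carry no information within strata. In rejection rates for that model this is at most about 1 point under the Table 1 effect, and roughly 2 to 5.5 points where the unstratified test has about 75% power.

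These figures depend on the assumed NIHSS and age distributions, the 60/40 split and the R² range, none of which the documents supply. Only NIHSS and age were examined, so nothing here supports adding other covariates. The primary test is valid and its planned power is unchanged.

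**What to change.** In Section 9.2.1.1, replace the sentence on multivariate regression with wording such as: the adjusted proportional-odds model will include the stratification factors together with Baseline NIHSS score and age as continuous covariates; these are prespecified as prognostic and will be included whatever balance is observed between the groups. Remove the imbalance rationale and the restriction to characteristics other than the stratification factors. Any further covariates can be listed in the SAP before the Day 90 lock of Section 9.2.3. Keep van Elteren as the primary test, with its present effect measure.

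The cost is small. No new data are needed and the code is standard. Because the sentence is protocol text, it goes through the amendment process of Section 12.1 and could travel with the next amendment. The adjusted odds ratio becomes conditional on NIHSS and age, so the report should explain why it differs from the strata-only estimate (in the R² = 0.3 example e^0.976 = 2.65 against e^0.905 = 2.47) and why its confidence interval on the log scale is not narrower.
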